EVALUATION OF A SIMULATION BASED WORKSHOP TO ENHANCE LEARNING OF INSERTION AND MANAGEMENT OF CSF DRAINAGE CATHETERS IN AN ANESTHESIA RESIDENCY PROGRAM

[name]; [name] M.D; [name]; [name] M.D

INTRODUCTION

Cerebrospinal fluid (CSF) drainage catheters have been increasingly used for monitoring and reduction of CSF pressure in a variety of neurosurgical and vascular procedures. [1, 2]

CSF drainage catheters have been shown to reduce the incidence of neurologic complications (paraplegia) after open and endovascular aortic surgery (references) and have been increasingly used especially with the FDA approval of thoracic endovascular stenting in 2007.

The use of lumbar CSF drainage catheters can result in serious complications, including the occurrence of bleeding, infection, over- drainage (with resultant subdural hematoma and herniation) and retained catheter fragments [3]. CSF related drainage complications can be reduced by following strict guidelines for introduction, maintenance and removal of these catheters [4].

With the expansion in the use of CSF drainage catheters, for thoracic endovascular and open aortic procedures, **the need arises for anesthesia trainees to learn the correct steps in insertion and management of CSF catheters, especially that complications arising from these catheters have been linked to faulty insertion techniques.**

Recent advances in educational and training technology are offering an increasing number of innovative and promising learning tools by simulation.

We thus propose to implement a simulation based training workshop for anesthesia residents to learn the technique of insertion and removal of CSF drainage catheters as well as the management of these catheters in the perioperative period. Few randomized controlled trials have been able to demonstrate the effects of simulation teaching in real-life patient care. This study aims to determine whether a simulation based workshop on CSF drainage catheters in thoracic aortic surgery prior to the cardiovascular anesthesia rotation results in better staff evaluations of residents and better patient care —a high stakes clinical setting, compared to standard operating room teaching

procedure on them such as venipuncture, lumbar puncture or central lines on them after they have undergone simulation training [15].

A prospective study conducted by Heinz et al aimed to determine whether simulation based training or an interactive seminar resulted in better patient care during weaning from cardiopulmonary bypass (CPB) a high stakes clinical environment. This is one study which determined the effectiveness of simulation training in the dynamic domains of anesthesiology. The study involved 20 anesthesiology trainees, postgraduate year 4 or higher inexperienced in CPB weaning, and 60 patients scheduled for elective coronary artery bypass grafting were recruited. Each trainee received a teaching Syllabus for CPB weaning 1 week before attempting to wean a patient from CPB (pretest). One week later, each trainee received a 2-h training session with either high-fidelity simulation-based training or a 2-h interactive seminar. Each trainee then weaned patients from CPB within 2 weeks (posttest) and 5 weeks (retention test) from the intervention. Clinical performance was measured using the validated Anesthesiologists' Nontechnical Skills Global Rating Scale and a checklist of expected clinical actions. They found that compared with traditional interactive seminars, simulation-based training was superior in achieving clinical skills needed for weaning a patient from CPB [16].

Simulation in today's era of medical education provides a medium and mechanism for clinical skill instruction. The environment allows for relevant, active learning with feedback, these being important components of clinical skill development and creates a safe environment for practicing new technologies without endangering patient or practitioner safety. As simulation becomes increasingly prevalent in medical school and resident education, more studies are needed to see if simulation improves patient outcomes [17].

The procedure of CSF drainage for thoracoabdominal and thoracic aneurysm repair (open and endovascular) has been associated with improved neurological outcomes as detailed earlier in this text. However, the procedure itself is associated with morbidity and mortality. Anecdotal case reports have reported a number of complications related to directly to the CSF catheter insertion and drainage. [18] [19] Observational studies have also cited a number of complications, namely, meningitis, epidural and subdural hematomas and nerve paresis due to the spinal drain placement.[20] The CSF catheter-related complications occurred in 1.5% (17 of 1,107) of patients. No spinal hematomas were observed. The CSF leaks with spinal headache, CSF leak without spinal headache, spinal headache, intracranial hemorrhage, catheter fracture, and meningitis occurred in 6 (0.54%), 1 (0.1%), 2 (0.2%), 5 (0.45%), 1 (0.1%), and 2 (0.2%) cases, respectively. Mortality from subdural hematoma was 40% (2 of 5), and from meningitis was 50% (1 of 2). Spinal headaches resolved with conservative *management*. All CSF leaks resolved, but 71% (5/7) required blood patches [1].

The learning curve for the CSF drain placement procedure is certainly very steep and the simulator would be the best first place to commence the learning process. The consequences of complications of this procedure are far reaching on the patient in terms of neurological deficit. Frequently, misadventures with the CSF drainage catheter, leads to situations where the vascular surgical procedure is cancelled or postponed, leading to wastage of precious healthcare dollars and clinical productivity.

STUDY OBJECTIVES

Our goal is to evaluate if a simulation based workshop on CSF drainage catheters would enhance learning based on STAFF EVALUATIONS at the end of their cardiac/vascular rotation. We will compare with a group of residents who did not undergo this training but underwent standard teaching in the operating room.

Primary Outcome

Staff evaluation after first spinal drain placement by the resident during the rotation based on an Anesthesiologist's Nontechnical Skills Global Rating Scale (scored from 1-4). The number of staff evaluating will be 5-6 staff who have expertise in vascular anesthesia.

Secondary outcome- Descriptive outcome

We will document the complications occurring due to the placement of CSF drainage catheters. We will not compare between the groups but use it just as a descriptive outcome.

METHODOLOGY

This study will be to evaluate the benefit of addition of a simulation based workshop on CSF drainage systems in the curriculum of anesthesia residents and compare it with residents who undergo the standard teaching and training program during their cardiovascular rotation.

TYPE OF STUDY

This is a parallel group randomized controlled trial which would allocate each resident into either the simulation or no simulation group.

RANDOMIZATION:

The study design allocates the whole group of residents in the vascular rotation (CA2s and CA3s), during a particular month, into one of the two groups (stimulation or no-stimulation). This would be achieved by randomizing each month into- simulation or no-simulation group. Randomization would be achieved by computer generated random number and would be communicated to the PI, who would facilitate the decided group specific educational plan for that month's resident group.

METHODS

During the first week of the vascular rotation, the residents randomized to the simulation group will be taken to the SIM center. There will be initial orientation and debriefing at the sim center.

The scenario consists of a patient requiring perioperative CSF drainage prior to undergoing thoracic aortic aneurysm surgery. The simulation will involve step by step instructions on insertion of the CSF drainage catheter including aseptic technique, position of patient (lateral vs. sitting), site of insertion. The simulation training will be done on a mannequin to simulate actual conditions. We plan to use a simulation model, which is basically a torso with the ability to palpate the back and spinous processes and use the epidural needle with loss of resistance technique with haptic feedback. The trainees would be able to actually perform the procedure on the manikin.

Various commercial CSF drainage kits are available. We will use the Medtronic lumbar drainage kit, which is available in the OR. Sterile technique, including chlorhexidine prep, full gown, sterile drape, sterile gloves, mask, hat. Insertion is typically at L3-L4 or L4-L5. The Touhy needle will be inserted with the bevel facing cephalad in incremental fashion with loss of resistance technique until the epidural space is reached and then inserted further till a distinct pop is felt and the subarachnoid space entered. This will be confirmed by free flow of CSF from the Touhy needle. The CSF catheter will then be inserted through the Touhy needle, taking care to avoid marked seepage of CSF by minimizing the duration between trocar withdrawal and catheter introduction. The technique of using wire reinforced catheters as opposed to ordinary catheters will be demonstrated (available on Integra CSF drainage catheters). The catheter will be threaded approximately 5 to 7 cm past the needle into the intrathecal space, the needle will be gently removed and the catheter secured with a clear occlusive dressing. Confirmation of free CSF drainage is obtained prior to dressing.

The simulation would continue needing assembly and attachment of the catheter to the monitor through a transducer and learning how to drain the CSF at a particular preset value. **The following would be discussed**

- Initial CSF pressure goal 10-12 mmHg
- Zeroing the transducer at the level of the right atrium
- Do not drain more than 20 ml/hr – risk of subdural or sub-arachnoid hematoma or brain stem herniation
- If CSF turns bloody - turn off drain and do not use it
- Patients should be transported with the drain turned off and catheter closed at two locations.
- Complications would all be addressed at this point
- New onset weakness: drain as above
- Optimize MAP
- If there is no demonstrable neurologic weakness for 72 hours of lower extremities, drainage is stopped and the CSF drainage catheter capped.

Lumbar Puncture & Epidural Trainer at the Sim center

Lumbar Puncture / Epidural Trainer (3)

This model is an ultrasound compatible trainer that includes the lumbar vertebrae, iliac crest, spinous process, ligamentum flavum, the epidural space and dura.

Becker's Drainage System-Medtronics

Anesthesiologist's Nontechnical Skills Global Rating Scale

Despite worldwide adoption of patient simulation in anesthesiology, there remains a lack of validated and reliable simulation performance assessment tools. Although most of the literature has focused on assessment of knowledge and technical skills during anesthesia simulation, research on nontechnical skills has become a recent area of interest. A comprehensive and reliable nontechnical skills assessment tool called the *Anaesthetists' Non-Technical Skills (ANTS) system* has recently been developed.

The hierarchical ANTS scoring system consists at the highest level of four basic skill categories, namely task management, team working, situation awareness, and decision making. These skill categories are further divided up into 15 skill elements. Each element is anchored for rating with examples of behaviors indicating good and poor practice. These skills are not necessarily acquired through clinical experience and may need to be specifically taught. Hence our primary outcome is based on this scale with a rating of 1-4.

Sub scores	Elements	Partial Rating	Global Category Rating
Task management	Planning and preparing Prioritizing Providing and maintaining standards Identifying and utilizing resources		
Team working	Coordinating activities with team Exchanging information Using authority and assertiveness Assessing capabilities Supporting others		
Situation awareness	Gathering information Recognizing and understanding Anticipating		
Decision-making	Identifying options Balancing risks and selecting options Reevaluating		

Rating Options Descriptor

4—Good Performance was of a consistently high standard, enhancing patient safety; it could be used as a positive example for others

3—Acceptable Performance was of a satisfactory standard but could be improved

2—Marginal Performance indicated cause for concern, considerable improvement is needed

Check List

Test Items	Test Items	Done	Partially done	Not done	Max Score possible
Task management	Obtained all the correct equipment for the setup	2	1	0	2
Task management	Observed sterile precautions	2	1	0	2
Team working	Appropriate communication with patient and assistants at the time of the procedure	2	1	0	2
Team working	Appropriate care of the catheter during shifting to ICU	2	1	0	2
Situation awareness	Identifies indications and advantages of CSF drainage catheter placement	2	1	0	2
Situation awareness	Appropriate leveling of the catheter to the right atrium.	2	1	0	2

6. *Blaisdell FW, Cooley DA: **The mechanism of paraplegia after temporary thoracic aortic occlusion and its relationship to spinal fluid pressure.** Surgery 1962, **51**:351-355.*

aortic disease undergoing advanced endovascular therapy. Vasc Endovascular Surg 2013, 47(6):415-422.

Approval: 31 May 2018

Title: Evaluation of a Simulation Based Workshop to Enhance Learning of Insertion and Management of CSF Drainage Catheters in an Anesthesia Residency Program

PI: [name]

SAP – NCT03545984

Following Institutional review board approval, CA-3 residents rotating through the vascular rotation at the Cleveland Clinic main campus in the period between December 2014 and June 2017 were randomly allocated to simulation based learning versus problem based learning using computer generated randomization. The learning activity (whether simulation based or problem based) was scheduled to occur in the first week of the vascular rotation and the content of the educational activities (simulation based and problem based) was designed to cover the same educational material.

The primary outcome was the composite score (modified Anesthesiologist's Nontechnical Skills Global Rating Scale) achieved by participating residents during their first CSF drainage catheter insertion and management as evaluated by their supervising cardiothoracic anesthesiologists. Evaluating staff anesthesiologists were blinded to the residents' allocation group and were not involved in the study.

Baseline and outcomes data were prospectively collected on 28 residents and respective patients undergoing thoracic aortic vascular procedure requiring CSF drainage catheters at the Cleveland Clinic main campus during the study period.

First, balance on potential confounding variables between two study groups were evaluated by using standard univariable summary statistics as well as by using absolute standardized difference scores (absolute difference in means, mean ranking, or proportions, divided by a pooled estimate of standard deviation among the two groups). Potential confounding variables exhibiting a standardized difference score of 0.20 or greater are supposedly imbalance and used for adjustment in primary analysis.

As the primary analysis, the effect of simulation versus problem based learning on staff evaluation outcome was assessed using multivariate proportional odds logistic regression model adjusting for imbalanced baseline variables. The odds ratio (along with 95% the confidence interval) estimated the odds of a better score with simulation versus traditional training in the operating room.

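### With 28 residents, the 0.20 imbalance rule admits about 60% of baseline variables by chance, so allocation noise largely sets the covariates of the primary model

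*Combined protocol and SAP*

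**What the plan says.** The SAP describes the data set as follows: "Baseline and outcomes data were prospectively collected on 28 residents and respective patients". Residents "were randomly allocated to simulation based learning versus problem based learning using computer generated randomization"; the Randomization section of the protocol makes the calendar month the unit: "This would be achieved by randomizing each month into- simulation or no-simulation group".

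The balance paragraph of the SAP states that "balance on potential confounding variables between two study groups were evaluated by using standard univariable summary statistics", and also by absolute standardized differences, defined as "absolute difference in means, mean ranking, or proportions, divided by a pooled estimate of standard deviation among the two groups". It then sets the rule at issue: "Potential confounding variables exhibiting a standardized difference score of 0.20 or greater are supposedly imbalance and used for adjustment in primary analysis". The last paragraph of the SAP makes the primary analysis a "multivariate proportional odds logistic regression model adjusting for imbalanced baseline variables".

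The SAP text does not name the candidate variables, fix any covariate in advance, limit the number of terms, give the arm sizes or relate the 0.20 threshold to the sample size.

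**The concern.** Under random allocation, any baseline difference between the arms is chance. A fixed threshold on the standardized difference can flag an unusual imbalance only if it is large relative to chance variation, and with 28 residents chance variation is wide. The trigger also never looks at how strongly a variable predicts the evaluation score, so relevant and irrelevant candidates have the same chance of entering.

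At stake is the adjusted odds ratio that the SAP treats as the trial's main result. Selection uses baseline data and allocation, not the outcome, so this is not outcome-driven model picking. The damage comes from loading an ordinal model on 28 observations with an uncontrolled number of parameters. In addition, the meaning of an adjusted odds ratio changes with the covariates conditioned on, and here those are settled by the particular allocation drawn.

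**Working it through.** **Inputs.** From the SAP: 28 residents, threshold 0.20, difference divided by a pooled SD, random allocation, proportional odds model. Assumed: a 14:14 split (others checked), and 3, 5 or 8 candidate variables.

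**The plan's own figures.** The documents give no error rate for the trigger. The only figures to reproduce are the detectable differences in the protocol's sample size section (1.53, 1.23 and 1.05 for 20, 30 and 40 residents). A two-sided t-test at 90% power gives 1.534, 1.226 and 1.052, so they reproduce. They do not bear on the trigger.

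**Chance rate, continuous variable.**
- Standard error of the standardized difference: sqrt(1/14 + 1/14) = 0.378.
- Threshold in standard errors: 0.20/0.378 = 0.53.
- 95% chance range: ±1.96 × 0.378 = ±0.74.
- P(|t| ≥ 0.53) on 26 degrees of freedom = 0.601.
- Other splits: 0.605 at 12:16, 0.616 at 10:18, 0.651 at 7:21.
- The median chance imbalance at 14:14 is 0.26, already above the trigger.
- For 0.20 to fire only 5% of the time, the total needed is 4 × (1.96/0.20)² ≈ 384 residents.

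**Other variable types.** Permutation gives 0.60 for rank-based variables. Exact binomial enumeration for binary variables gives 0.55 to 0.67 over prevalence 0.2 to 0.5 and splits 14:14, 12:16 and 10:18. If baseline variables cluster by month, a design effect of 1.1 to 1.5 raises the 14:14 normal-approximation rate from 0.597 to between 0.614 and 0.666.

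**Consequences.** For k independent candidates, the expected number entering is 0.601k and the chance that none enters is 0.399^k. The remaining rows come from a maximum-likelihood proportional odds simulation: 14:14, 3,000 runs per setting, a four-level outcome, independent standard normal candidates, and one prognostic candidate with log-OR 0.8 per SD. The Monte Carlo error of the type I rates is about 0.4 to 0.5 points.

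| | k = 3 | k = 5 | k = 8 |
|---|---|---|---|
| Expected number entering | 1.8 | 3.0 | 4.8 |
| Chance that none enters | 6.3% | 1.0% | 0.06% |
| SD of null log-OR: 0.20 rule | 0.847 | 0.923 | 1.100 |
| SD: one fixed prognostic covariate | 0.823 | 0.814 | 0.824 |
| SD: one fixed non-prognostic covariate | 0.798 | 0.799 | 0.804 |
| Type I, Wald: 0.20 rule | 5.4% | 6.1% | 7.5% |
| Type I, Wald: fixed prognostic | 5.8% | 6.3% | 5.9% |
| Type I, Wald: fixed non-prognostic | 5.7% | 5.7% | 5.8% |
| Type I, LRT: 0.20 rule | 6.3% | 7.3% | 9.1% |
| Type I, LRT: fixed prognostic | 7.2% | 7.8% | 7.3% |
| Type I, LRT: fixed non-prognostic | 6.8% | 6.6% | 7.0% |
| Median estimate, true log-OR 1.5: 0.20 rule | 1.58 | 1.62 | 1.74 |
| Median estimate: fixed prognostic | 1.62 | 1.59 | 1.64 |

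Against the fixed prognostic covariate, the SD ratios are 0.847/0.823 = 1.03, 0.923/0.814 = 1.13 and 1.100/0.824 = 1.33. Against the non-prognostic one they are 1.06, 1.16 and 1.37. At 10:18 with 8 candidates, the rule gives SD 1.12, Wald 7.0% and LRT 8.8%, against 0.86, 5.8% and 6.6% with the fixed prognostic covariate.

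A separate 500-run simulation agrees. The SDs, rule against fixed prognostic, are 0.81 v 0.79, 0.86 v 0.76 and 1.06 v 0.82. At 8 candidates the LRT type I error is 10.2% v 7.8% and the median estimate 1.80 v 1.63.

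**The case against.** The firing rate is not in dispute. The case on the other side concerns consequence and remedy.

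- **The harm depends on an unknown number.** At 3 or 5 candidates, type I error under the rule does not differ from a fixed covariate beyond simulation error. This stands. At 5 the loss is in precision only, and the type I and bias effects belong to about 8.
- **A candidate list may exist elsewhere.** The protocol's analysis text begins abruptly in the copy reviewed, so a list may have been lost there. This is possible. The SAP text itself has none. A list would settle how much harm applies but would not change the 60%.
- **Calling the candidates potential confounders implies prognostic judgement.** Judgement may have shaped the list, but it does not decide which listed variables enter. With all candidates moderately prognostic, the spread at 5 still rose by about 12%.
- **A predictor is omitted only when its imbalance is below 0.20, where it distorts least.** This is correct as regards confounding. The precision it would have brought is still lost, and the odds ratio is on a different scale.
- **SD of the log-OR is an imperfect measure.** In one run at 5 candidates the unadjusted model had the smallest SD (0.76, against 0.82 with a fixed prognostic covariate), because adjustment changes the scale. This is a fair caution. However, in the 500-run simulation the fixed prognostic covariate also had about 4 to 5 points more power than the rule. The Monte Carlo error there is about sqrt(0.25/500) = 2.2 points per rate, so the conclusion does not rest on that gain. Against a non-prognostic covariate, Wald power at 8 candidates is level (47% v 48%), so no power loss is claimed.
- **The simulated outcome is assumed.** With 12 levels in place of four, the SD at 5 candidates fell from 0.94 to 0.88, with similar relative inflation. The simulations treat residents as independent.
- **A late change adds discretion, whereas the rule is mechanical and blind to outcome.** This is a real cost. It is the reason to choose blind, disclose the change and keep the 0.20-rule model visible.

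**Conclusion.** The concern holds. At this sample size the 0.20 trigger fires on about 60% of randomised continuous or rank-based variables (0.60 to 0.65 for splits from 14:14 to 7:21) and on roughly 55% to 67% of binary ones. It therefore does not separate notable imbalance from ordinary chance, and it decides covariates without regard to prognosis.

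The firing rate is firm because it depends only on the 28 residents and, weakly, on the unstated split. The effect on the primary odds ratio is conditional on the number of candidates: slight at 3, a clear loss of precision at 5, and at 8 also a shift away from the null and a modest rise in type I error. Those sizes rest on the simulated outcome scale, independent residents and candidates, and a single prognostic variable. From the SAP text a reader cannot tell which case applies. This warrants correction but does not invalidate the trial.

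**What to change.** 1. Keep standardized differences as a description of the groups, with no role in choosing the model.
2. Replace the trigger with at most one or two covariates from the baseline data already collected, chosen on prognostic grounds without reference to observed imbalance or outcome, ideally by someone who has seen neither. If data have been seen, disclose this as a late change.
3. Report the unadjusted treatment comparison beside the adjusted one.
4. Retain the 0.20-rule model as a sensitivity analysis, with the full list of candidates and a statement of which entered.

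The cost is SAP wording, one disclosed change and two extra model fits on existing data; no new data are needed. There are two downsides. A variable imbalanced by chance is handled in the sensitivity analysis and not in the primary model. A late covariate choice also adds some discretion, which the disclosure and the unadjusted result keep open to inspection.

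### The SAP gives its single primary odds ratio two different comparators, and the text provided does not explain the change from the protocol's comparator

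*Combined protocol and SAP*

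**What the plan says.** The SAP's opening paragraph states that residents "were randomly allocated to simulation based learning versus problem based learning using computer generated randomization". Both activities were scheduled for the first week of the rotation, and "the content of the educational activities (simulation based and problem based) was designed to cover the same educational material".

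The SAP's final paragraph, on the primary analysis, first says that "the effect of simulation versus problem based learning on staff evaluation outcome was assessed using multivariate proportional odds logistic regression model", with adjustment for imbalanced baseline variables. Its next and last sentence says that the odds ratio from this model "estimated the odds of a better score with simulation versus traditional training in the operating room".

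The protocol describes the control differently. The Introduction sets the workshop's effect "compared to standard operating room teaching". Study Objectives says "We will compare with a group of residents who did not undergo this training but underwent standard teaching in the operating room". Methodology says the study will "compare it with residents who undergo the standard teaching and training program during their cardiovascular rotation", and Type of Study says the trial "would allocate each resident into either the simulation or no simulation group".

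**The concern.** A two-group odds ratio has one reference group, and the two sentences that define the primary effect measure name two. The second of them names a control to which, on the SAP's own description, nobody was randomised.

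The two controls answer different questions. Against standard operating-room teaching, the trial asks whether adding a workshop improves the resident's first catheter placement; this is the goal stated in Study Objectives. Against a content-matched problem-based session, it asks whether the simulation format does better than another format teaching the same material. A reader who takes the last SAP sentence at face value would read the result as an answer to the first question when the design in the SAP addresses the second.

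**Working it through.** No arithmetic settles this point, so the check is a comparison of the relevant text.

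**1. Number of groups.** The SAP's paragraph on baseline balance refers to two study groups, and no third arm is described anywhere. The primary model therefore yields one treatment odds ratio with one reference group.

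**2. Which reference group.**

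| Place | Control named |
|---|---|
| Protocol, Introduction | Standard operating-room teaching |
| Protocol, Study Objectives | No workshop; standard operating-room teaching |
| Protocol, Methodology | Standard teaching and training program |
| Protocol, Type of Study and Randomization | No simulation |
| SAP, opening paragraph (allocation) | Problem-based learning, same week and same content |
| SAP, final paragraph (model sentence) | Problem-based learning |
| SAP, final paragraph (odds-ratio sentence) | Traditional operating-room training |

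**3. Tally of the wording.**
- SAP: problem-based teaching as the control 4 times (3 in the opening paragraph, 1 in the model sentence); traditional operating-room training once.
- Protocol: standard teaching as the comparator 3 times; no simulation 3 times (once misspelled as no-stimulation); problem-based teaching 0 times.

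The tally shows that the odd label in the SAP matches the protocol's comparator. It does not measure the consequence.

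**4. Whether the labels could mean the same thing.** The SAP presents problem-based learning as a separate scheduled activity designed to match the simulation content. Study Objectives describes controls who had only operating-room teaching. No sentence in the text provided equates the two.

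**5. What the odds ratio can support.** Write S for simulation, P for problem-based learning and T for traditional operating-room teaching. If one proportional odds model held for all three conditions, then

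log OR(S vs T) = log OR(S vs P) + log OR(P vs T).

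Allocation as the SAP describes it identifies only log OR(S vs P). Nothing in the trial estimates log OR(P vs T). If log OR(S vs P) = 0, then log OR(S vs T) = log OR(P vs T), which could be zero or large: both sessions might help equally. If log OR(S vs P) is positive, it equals log OR(S vs T) only when log OR(P vs T) = 0, and the trial has no data on that.

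**6. Sample-size figures.** The detectable differences under Sample size considerations (1.53, 1.23 and 1.05 for 20, 30 and 40 residents) reproduce as 1.534, 1.226 and 1.052. This uses a two-sided t-test at 0.05, 90% power, SD 1 and equal arms (two-sidedness and equal arms assumed). That calculation does not involve the control's label and has no bearing on this point.

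**The case against.** The strongest reply is that the last phrase is a leftover from the protocol. The SAP defines its two groups once, in specific terms, and the model sentence repeats that contrast. With no third arm, there is no doubt which coefficient is estimated, and its value does not change. This is a likely explanation of how the phrase arose, but the sentence that states what the primary odds ratio means still names the wrong control if the allocation paragraph is right.

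A second reply is that every resident was on the vascular rotation, so both arms plausibly had routine operating-room teaching. The protocol's reference to a standard program and a group-specific educational plan might also leave room for a structured control session. The documents do not say so. Even if both arms had such teaching, it would be common background and would not become the contrast.

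A third reply concerns missing text. The public file has gaps; for example, the protocol refers to analogous methods for secondary outcomes without a preceding primary method. An explanation of the changed comparator may have stood in text we do not have. That limit stands: the finding is only that the text provided gives no explanation. It does not touch the conflict between two adjacent SAP sentences.

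Finally, the SAP is written in the past tense about data already collected on 28 residents. The practical remedy therefore lies in correcting the SAP wording and in how the result is reported, not in how the trial is run.

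**Conclusion.** The concern holds, and the SAP is wrong as written. The value of the primary odds ratio is unaffected; the contrast it is said to estimate is misstated in one of two adjacent sentences. If the allocation paragraph is correct, the trial supports a statement about simulation against problem-based teaching of the same material, and none about simulation against traditional operating-room training. The comparator also differs between protocol and SAP, which changes the question asked, and no reason is given in the text provided.

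The conflict within the SAP rests on no assumption beyond the two sentences themselves. Which sentence is wrong depends on what the control arm received, and only the trial records can show that. The correction should be made before the result is reported or relied on.

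**What to change.** 1. Confirm from trial records which control was delivered, and use that single label in the SAP's allocation, model and odds-ratio sentences.
2. If it was problem-based learning, replace the comparator at the end of the odds-ratio sentence with problem-based learning. Limit the conclusion to simulation against problem-based teaching of the same material. Record in the SAP and the report a dated explanation of when and why the comparator departed from the protocol, leaving the original protocol text as it stands.
3. If it was standard operating-room teaching, correct the SAP's design paragraph and its model sentence instead.

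The cost is a check of trial records, a few wording changes and, if the comparator changed, one dated note. No new data and no re-analysis are needed.
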